Enhanced REP (enREP) Activities. EnREP begins with the same activities as foundational REP. Sites that were initially randomized to the enREP group and do not meet EBP-specific a priori benchmarks reflecting adoption within 6 months will continue with foundational REP and will receive higher intensity support for a period of 4-6 months (enREP). The higher intensity support will consist of tailored sessions including a barrier/needs assessment and facilitation, a process of interactive problem solving and support that occurs in a context of a supportive interpersonal relationship.³⁷ Sites will participate in a minimum of 3 to 4 sessions with additional sessions available upon a site's request. Sites will be asked to selfidentify and rank perceived barriers to implementation. Facilitators will follow an evidenceinformed table specifying identified barriers to implementation, along with potential aligned strategies to overcome the barriers, and examples in the context of the EBP. Facilitation will be provided by Function QUERI team members who are experts in implementation and have close collaborations with EBP content experts (for example, the Durham VA physical therapist who leads Group PT classes). Each call will be attended by additional members of the research team who will listen and take structured notes regarding call fidelity monitoring and implementation tracking. Facilitators' actions will depend on each site's needs and clinical context. As a specific example, if a site reports problems with documenting information in the EHR, then the facilitator could forge connections between a CAC working with the research team and a CAC at a site. Based on our current work, we anticipate facilitators will help sites engage facility leadership, provide resource materials, identify and address barriers to program launch, and support marketing efforts. EnREP may include CONNECT, a complexity sciencebased bundle of interaction-oriented activities designed to supplement implementation efforts by promoting team function and readiness for change.²² CONNECT may be included as a component of implementation intensification because of its specific focus on building skills to optimize team function, which complements activities of facilitation. ^{22,38-40} All three EBPs rely, in different ways, on interactions across different types of providers and clinical services, making team function and communication essential for successful implementation. Therefore, we propose that CONNECT will be specifically relevant for sites that do not exhibit successful EBP adoption and express challenges around team communication. Our prior Function QUERI work found that CONNECT was viewed as helpful for understanding communication patterns and breakdowns across service lines and facilitating cross-service interactions, but that it could be improved by identifying key players to facilitate effective communication and engaging team members throughout the implementation process. Based on these findings, CONNECT can be tailored for each EBP and challenges of individual sites, utilizing a menu of activities we have experience with: relationship mapping of communication patterns, identification of key crossservice communicators, strategies for creative, ongoing problem solving, and mentorship to sustain new interaction behaviors.38

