Group PT and STRIDE will randomize sites 1:1 to foundational REP or enREP, which consists of adding higher intensity implementation support for VAMCs that do not meet adoption goals at 6 months nor sustainment goals at months 8 and 9 (for STRIDE and GPT, respectively). The Caregiver FIRST design is slightly different to take advantage of the fact that CSP requested national implementation to address unmet needs for training and to support the expansion of general caregiver services required by the MISSION Act. Following Caregiver FIRST roll-out at all 150 medical centers, we will enroll a subset of sites that did not meet a priori adoption benchmarks at 6 months (n=24) and randomize them 1:1 to continue foundational REP or receive higher intensity implementation support. A run-in design is critical for this project for efficient use of resources because we cannot forecast which sites will be able to launch the mandatory EBP independently and which will need a more intensive approach to adopt the EBP. All projects use a common set of foundational REP activities and higher intensity strategies. Primary outcomes will be assessed at project specific time points between 10-18 months from the beginning of foundational REP, based on previous experience of how long it takes to implement each EBP.

[figure not shown]

Figure 3. Function QUERI Project Design Overview

Implementation Project 1: Group PT for Knee OA

Urgency of improving functional outcomes in Veterans with knee OA and relationship to ICF. Knee OA is a common and often disabling health condition that affects 14 million people in

Objective	Improve access to PT to Veterans with knee osteoarthritis by delivering PT in a group setting
Evidence	Allen et al. Group Versus Individual Physical Therapy for Veterans With Knee Osteoarthritis: Randomized Clinical Trial. Phys Ther 2016, 96:597-608.
Primary Partners	VA Physical Medicine & Rehabilitation Program

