Leadership. [name] is a health services researcher, an exercise scientist, VA HSR&D Research Career Scientist and Associate Director of the Durham HSR&D Center of Innovation to Accelerate Discovery and Practice Transformation (COIN ADAPT). She is an expert in pragmatic and implementation-focused trials of rehabilitation interventions, with an emphasis on functional outcomes.

Implementation Project 2: STRIDE

Urgency of addressing hospital-associated disability and relationship to ICF. Hospitalization is a major (environmental) risk factor for development of disability. More than one-third of adults over the age of 70 are discharged from the hospital with a major new

Objective	Hastings et al. Assisted early mobility for	
Evidence		
Primary Partners	Geriatrics and Extended Care	VHA Diffusion of Excellence

disability that was not present before the onset of acute illness.⁶ A key contributor to hospital-associated disability is immobility during hospitalization.⁷⁶ Although fewer than 5% of patients have physician orders for bed rest, hospitalized older adults spend only about 3% of their time standing or walking.⁷⁷ The hazards of bedrest have been recognized for more than 2 decades,⁷⁸ but there remains a persistent 'epidemic of immobility' in American hospitals.⁷⁹

Project Goal. The overall goal of the project is to implement, evaluate and sustain STRIDE in at least 32 additional VAMCs. We will address the following specific aims:

Specific Aim 1: Develop scalable approaches to implement and sustain STRIDE.

Key questions: What are stakeholder perspectives on key elements of a large-scale dissemination plan? How should the STRIDE clinical program be adapted to optimize sustainability?

Specific Aim 2: Evaluate implementation with foundational REP versus enhanced REP.

Key questions: Are there differences in implementation outcomes (penetration, fidelity) at 10 months (primary), 13, and 16 months between arms? What is the impact on effectiveness outcomes and quality metrics (hospital length of stay or discharge to nursing home) at implementing sites? How do sites experience implementation strategies in each arm? What baseline organizational characteristics are associated with sites that do not meet implementation benchmarks?

Study design and methods

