In the CRT to address Aim 2 we will randomize sites 1:1 to either foundational REP or enREP (Fig. 3). In partnership with Diffusion of Excellence, we will invite all VISN Directors to encourage medical centers within their region to start STRIDE programs. This approach has worked well within VISN 6, and other VISNs have agreed to participate. Additionally, we will utilize Microsoft Identity Manager to compile a list of professionals by job title who may be willing to implement STRIDE at their facilities. We will reach out to them via email or Microsoft TEAMS to gauge interest. Sites will be enrolled in cohorts with the goal of enrolling at least 32 sites. We plan on conducting a stratified randomization⁸⁰⁻⁸³ with the following site level covariates assessed prior to randomization: facility complexity level (1a complexity vs. all others), general medicine adjusted length of stay (adjusted length of stay ≥ 4.7 days vs < 4.7 days), and whether the hospital has previously attempted to start a mobility program or received resources to start STRIDE (yes to either vs. no).. These characteristics were chosen to represent factors likely to be associated with baseline differences in sites that may affect implementation outcomes-low bandwidth, presence of local innovations, competing priorities and needs alignment.⁸⁴ General medicine adjusted length of stay will be captured using the Strategic Analytics for Improvement and Learning Value Model (SAIL) which assess key quality measures as well as overall efficiency at individual VAMCs. Previous experience with mobility programs will be determined by standard intake forms completed by POCs at each hospital asking if (1) anyone at their facility previously tried to start a STRIDE or other mobility program on a general medicine ward in the past five years and (2) if they have received resources or other staffing support from their VISN or a VA program office to start a STRIDE program. Implementation activities. Foundational REP activities have been described previously. EnREP begins with the same activities as foundational REP. After 6 months, sites randomized to enREP that do not meet adoption benchmarks (defined as 5 general medicine patients with a STRIDE walk in months 5-6; assessed at the end of month 6 will receive higher intensity support sessions for 4-5 months (depending on site availability), consisting of the site implementation team and a Function QUERI facilitator. Sessions will be scheduled in collaboration with the site to promote interactive problem solving in the context of a supportive interpersonal relationship. At the completion of the Function QUERI study, all participating STRIDE sites will receive a thank-you email and small gift bags to be shared among team members (e.g., water bottles, lunch box, t-shirts, hats,

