
etc.) to show appreciation. STRIDE sites will be unaware that they will receive a thank-you gift bag and therefore would not be considered as an incentive for study participation.

Patient sample. Clinical criteria for STRIDE participation at each site will include: Age >= 60, admission for medical illness, community-dwelling (i.e. not in a nursing home), not requiring inpatient physical therapy, ability to follow one-step commands and to ambulate safely and independently.

Outcomes. Implementation outcomes. Penetration (primary outcome) is defined as the proportion of eligible hospitalizations with at least one documented STRIDE walk. It is not possible to assess all eligibility criteria in the EHR (e.g. able to walk at baseline); thus, with this more inclusive denominator, 100% penetration is not an appropriate goal. Based on preliminary data, we anticipate penetration to range from 0% (no program activity at 10-month outcome assessment) to 40% (estimated maximum achievable based on data from current STRIDE sites). Fidelity will be assessed for eligible hospitalizations with at least one documented STRIDE walk as the percentage of eligible hospital days with "full dose" of the program, defined as two or more documented walks or one for more than five minutes. Program adoption is defined as ≥ 5 general medicine patients with a STRIDE walk in the EHR within month 5 or 6 from start date with Function QUERI. We will assess implementation outcomes at 10 months (primary), as all current STRIDE sites have launched within this time frame, and also at 13, and 16 months to describe trajectories and assess sustainment, given that we have observed the dynamic nature of STRIDE program activity at some sites.

Effectiveness Outcomes/Quality metrics: Consistent with previous literature on the impact of hospital walking programs we will focus on hospital **length of stay** (LOS) due to its importance to patients and implications for overall facility efficiency and performance reporting (e.g., SAIL measures). Other important effectiveness outcomes will include inpatient fall rates (assessed using Inpatient Evaluation Center or IPEC), and discharge to nursing home (defined using established procedures combining VA + Medicare data sources).

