Analyses. To address the question: How should the STRIDE clinical program be adapted to optimize sustainability? We will use the FRAME to classify STRIDE adaptations at 17 VAMCs that have started programs (via VISN 6 rollout, ongoing Function QUERI trial or other means). Data sources will include study team notes, communications, interview transcripts, and data collected on Diffusion Network calls. Responses will be coded and analyzed at site levels to develop facility-level summaries of STRIDE adaptations, indicating where there is divergence in responses at the site-level. From this coded data, we will identify and visually display emergent themes in a matrix, with columns reflecting implementation outcomes (i.e., fidelity and penetration) arranged from high to low, to illustrate patterns in program adaptations according to implementation outcomes. To address the question: Are there differences in implementation outcomes (penetration, fidelity) at 10 months (primary), 13, 16 months between arms? We hypothesize that sites randomized to enREP will have higher penetration (proportion of eligible patients with ≥ 1 STRIDE documented walk during hospitalization) and fidelity (eligible hospitalizations with at least one documented STRIDE walk as the percentage of eligible hospital days with "full dose" of the program, defined as two or more documented walks or one for more than five minutes.). We will use generalized linear models⁷⁵ to examine the effect of foundational vs. enREP on implementation outcomes at 10-months. The main predictors of interest will be foundational REP vs. enREP and stratification variables used in the covariate constrained randomization (described above). We will examine how fidelity and penetration outcomes change over time using descriptive methods (e.g. plots, descriptive statistics, subgroups). To address the question: What is the impact on effectiveness outcomes and quality metrics (hospital length of stay or discharge to nursing home) at implementing sites? In exploratory analyses, we are interested in assessing the impact of STRIDE on hospital LOS, discharge to nursing home, and inpatient fall rates. Our sample of Veterans for this analysis will

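### STRIDE asks about arm differences at 10, 13 and 16 months but plans a between-arm estimate only at month 10, which falls at or up to one month before the end of intensified support

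*Combined protocol and SAP*

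**What the plan says.** All references are to the combined protocol and SAP.

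- **Question.** Under Implementation Project 2: STRIDE, Specific Aim 2, the key question is: "Are there differences in implementation outcomes (penetration, fidelity) at 10 months (primary), 13, and 16 months between arms". It is repeated in the project's Analyses paragraph and under Data Analysis and Statistical Considerations.
- **Analysis.** Both analysis sections specify a generalized linear model for foundational REP versus enREP, with the stratification variables, for outcomes at 10 months. For the rest: "We will examine how fidelity and penetration outcomes change over time using descriptive methods".
- **Time points.** On the primary reading, the STRIDE Outcomes paragraph says: "We will assess implementation outcomes at 10 months (primary), as all current STRIDE sites have launched within this time frame". The two later readings are given a different role there: "and also at 13, and 16 months to describe trajectories and assess sustainment".
- **Sample size.** The STRIDE calculation is for outcomes at 10 months.
- **Support.** In the STRIDE Implementation activities paragraph, the adoption benchmark is "assessed at the end of month 6", and enREP sites that miss it "will receive higher intensity support sessions for 4-5 months (depending on site availability"). The common section on Enhanced REP activities instead says such sites "will receive higher intensity support for a period of 4-6 months (enREP"). The Implementation Projects overview adds a second trigger, for sites that "do not meet adoption goals at 6 months nor sustainment goals at months 8 and 9 (for STRIDE and GPT, respectively").

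**The concern.** The plan asks a between-arm question at three time points and supplies a between-arm analysis at one. For months 13 and 16 there is no model, no estimated arm difference and no interval.

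The timing of support makes this more than a wording matter. The arms differ only after month 6, so month 10 allows at most four months of contrast, and support may still be running. The reason given for month 10 is how long earlier sites took to launch. That does not address how long intensification, which starts after month 6, takes to change penetration, or whether a change lasts once support stops. Months 13 and 16 are the readings that speak to this. Without a pre-specified contrast, any arm difference reported at those months would be a post hoc choice of method.

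**Working it through.** **1. The plan's own power figure.** Inputs from the STRIDE sample size paragraph: 16 versus 16 sites, two-sided 5% t-test, SD 9 points, 80% power at effect size d = 1.0 (9 points) and 90% at d = 1.2 (10.8 points). Using the noncentral t with df = 16 + 16 − 2 = 30, critical value 2.042 and noncentrality d × √(16/2):

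| d | Noncentrality | Power | Stated |
|---|---|---|---|
| 1.0 | 2.83 | 78.1% | 80% |
| 1.2 | 3.39 | 90.7% | 90% |

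The figures reproduce to within 2 points. They refer to the difference at month 10.

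**2. When support ends.** Start: end of month 6.

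| Source | Duration | Ends | Share delivered by month 10 |
|---|---|---|---|
| STRIDE section, shorter course | 4 months | 6 + 4 = 10 | 4/4 = 100% |
| STRIDE section, longer course | 5 months | 6 + 5 = 11 | 4/5 = 80% |
| Common enREP section, upper end | 6 months | 6 + 6 = 12 | 4/6 = 67% |

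The overview's month-8 trigger has no duration in the STRIDE section. If it also led to 4–5 months (assumption), support would end at 8 + 4 = 12 to 8 + 5 = 13. The window over which penetration at 10 months is measured is not defined. A window opening before month 10 would overlap with support even on a 4-month course.

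**3. Question against analysis.**

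| Month | Arm difference asked about | Arm-effect model specified | Covered by sample size |
|---|---|---|---|
| 10 | Yes (primary) | Yes | Yes |
| 13 | Yes | No | No |
| 16 | Yes | No | No |

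**4. Precision at the later months.** Assume 16 sites per arm and an SD still at 9 points; the documents give no later SD. Standard error = 9 × √(1/16 + 1/16) = 3.18 points, and the 95% half-width is 2.042 × 3.18 = 6.5 points. The half-width scales with the SD: an SD 25% lower or higher gives 4.9 or 8.1 points. This ignores adjustment for strata.

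**5. Error control, if the later contrasts are tested.** Three unadjusted 5% tests would carry a family-wise error of up to 1 − 0.95³ = 14.3% under independence, and less with positive correlation. Splitting 5% equally over three time points would cut month-10 power for 9 points from 78.1% to 61.7%. A fixed order of 10, then 13, then 16 leaves month 10 at the full 5% and its power unchanged.

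**The case against.** Month 10 is a deliberate primary time point with a stated reason. The Outcomes paragraph openly gives months 13 and 16 a descriptive and sustainment role. With about 32 sites, confining formal inference to one time point is defensible. The overlap is also narrow: under the STRIDE section it is at most one month, and it touches only enREP sites that miss the benchmark and take the longer course. Descriptive statistics may well be shown by arm, although the STRIDE text does not say so.

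Most of this stands, and it is why month 10 should remain the sole primary. It does not remove the mismatch, because the same plan poses months 13 and 16 as a between-arm question in three places.

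A reader might go further and infer that month 10 captures only part of the effect, so that the primary test understates it and is underpowered. The documents do not support that. The 9-point difference in the sample size paragraph is set at month 10 and is not described as a later effect to be discounted. There is no build-up curve and no figure for the share of sites needing support. After support ends the arm difference could also fade, or narrow as foundational sites catch up, and month 10 could be its peak.

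**Conclusion.** The point holds as a gap between question and analysis. Arm differences are asked about at 10, 13 and 16 months, and a between-arm estimate is planned only at month 10. Two of the three time points lack an estimate and interval. On the STRIDE section's own durations, month 10 falls at the end of intensified support or one month before it, so the primary reading cannot show what happens to the arm difference afterwards.

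The primary analysis and its power statement are not undermined. Overlap with support is possible, not certain, and no direction of bias can be claimed. The mismatch does not depend on the overlap. The timing argument assumes that support starts directly after the month-6 assessment.

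**What to change.** - Keep the planned month-10 generalized linear model as the only primary analysis, at the full 5%.
- Fit the same model (arm plus stratification variables) to the month-13 and month-16 outcomes. Report the arm difference with its 95% confidence interval at each, labeled secondary. If these are tested, use the fixed order month 13 then month 16 after month 10.
- A repeated-measures model over the three months, with a small-sample correction, may be added as supportive. It should not replace the month-10 model.
- Make the same change in the STRIDE Analyses paragraph and under Data Analysis and Statistical Considerations.
- Reconcile the support durations and triggers in the common enREP section, the Implementation Projects overview and the STRIDE section, and define the measurement window for each time point.

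If the team does not want later contrasts, the minimum is to reword the key question so that months 13 and 16 are descriptive.

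The cost is analysis wording and two added secondary contrasts per outcome. The data are already planned and no sites are added. The drawback is wide intervals at about 32 sites, so the later results should be read as estimates and not as confirmatory tests.

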come from sites that adopt STRIDE (approximately 95,000 Veterans). The sample of Veterans will be from those who are hospitalized and meet our patient eligibility criteria; some of those patients will have participated in STRIDE (i.e. treatment group) and some will have not (i.e. comparison group). Data sources include CDW, VA/CMS repository data, GEC Health Care Risk measures and Geriatrics and Extended Care Data Analysis Center (GECDAC) Residential History File data. We will use inverse-probability of treatment weighted methods to adjust for confounding and estimate an average causal treatment effect for STRIDE. The study team will determine a priori which covariates are likely to be key determinants of receiving STRIDE. Qualitative data collection and approaches to data integration have been described previously.

Sample size estimate. Sample size calculations were conducted for the implementation outcomes at 10-months. Using a two-sided t-test based on a sample size of a minimum of 32 sites (at least 16 foundational REP and at least 16 enREP), a type-1 error rate of 5%, we will have 80% power to detect an effect size difference of 1.0 and 90% power to detect an effect size difference of 1.2 between arms. For the primary penetration implementation outcome, assuming a standard deviation of approximately 9% based on preliminary data from ongoing work, these effect size differences correspond to a mean difference of 9% between arms for 80% power and 10.8% for 90% power, with enREP having the higher penetrance.

Leadership. [name], a geriatrician, is the Corresponding PI for the Function QUERI program. [name] leads Durham's COIN ADAPT, and has substantial clinical, research and leadership expertise relevant to implementing and evaluating new clinical programs in VA.

Implementation Project 3: Caregivers FIRST

Urgency of expanding supports to family caregivers and relationship to ICF. 2 million Veterans with functional and/or cognitive impairment in VA receive informal care, e.g., care from a family member or friend, and this support is a key determinant of whether or not function and independence are preserved. These caregivers are currently

Objective	Improve caregiver and Veteran functioning through caregiver skill training and support
Evidence	Van [name] et al. Family caregiver skills training to improve experiences of care: a randomized clinical trial. J Gen Intern Med 2019 Oct;34(10):2114-2122.
Primary Partners	VA Caregiver Support Program

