subgroups). To address the question: What is the impact on effectiveness outcomes and quality metrics (hospital length of stay or discharge to nursing home) at implementing sites? In exploratory analyses, we are interested in assessing the impact of STRIDE on hospital LOS, discharge to nursing home, and inpatient fall rates. Our sample of Veterans for this analysis will come from sites that adopt STRIDE. The sample of Veterans will be from those who are hospitalized and meet our patient eligibility criteria; some of those patients will have participated in STRIDE (i.e. treatment group) and some will have not (i.e. comparison group). We will use inverse-probability of treatment weighted methods to adjust for confounding and estimate an average causal treatment effect for STRIDE. The study team will determine a priori which covariates are likely to be key determinants of receiving STRIDE. Qualitative data collection and approaches to data integration have been described previously.

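### STRIDE's exploratory effectiveness comparison may set patients who walked against a group that includes patients who could not walk, so weighting on recorded covariates does not support its causal claim

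*Combined protocol and SAP*

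**What the plan says.** Under Implementation Project 2: STRIDE, Patient sample, the clinical criteria include "not requiring inpatient physical therapy, ability to follow one-step commands and to ambulate safely and independently".

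Under Outcomes, in defining penetration, the protocol says: "It is not possible to assess all eligibility criteria in the EHR (e.g. able to walk at baseline". It draws the consequence there: "thus, with this more inclusive denominator, 100% penetration is not an appropriate goal". It expects penetration between 0% and an estimated maximum of 40%.

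Under Analyses, the effectiveness work is labelled exploratory. The Veterans "come from sites that adopt STRIDE (approximately 95,000 Veterans". The inclusion rule is "The sample of Veterans will be from those who are hospitalized and meet our patient eligibility criteria", and the contrast is "some of those patients will have participated in STRIDE (i.e. treatment group) and some will have not (i.e. comparison group". The method is: "We will use inverse-probability of treatment weighted methods to adjust for confounding and estimate an average causal treatment effect for STRIDE". Covariates are to be chosen in advance as determinants of receiving STRIDE, but none is listed. The data sources include GEC Health Care Risk measures. The section Data Analysis and Statistical Considerations repeats the inclusion rule, the contrast and the causal aim.

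Background and Significance describes STRIDE as one gait and balance assessment by a physical therapist, then supervised daily walks until discharge.

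**The concern.** The effectiveness analysis relies on an eligibility definition that the penetration outcome says cannot be fully applied in the EHR. The limitation is acknowledged for the penetration denominator and not carried over. Nothing says how ability to walk will be established for non-participants, and no mobility covariate is named.

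The two groups are therefore selected differently. Every participant walked. Non-participants are a mixture of eligible patients whom the program did not reach and patients who could not have walked. The second kind has zero probability of treatment. If the feature that sets them apart is unrecorded, a propensity model cannot find them, and weighting balances only what it sees.

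At stake is one of the STRIDE key questions, the effect on length of stay and nursing-home discharge at implementing sites. These results also feed the program's stated aim of assessing quality metrics to inform sustainment.

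**Working it through.** The plan gives no effect size, power or eligible share for this analysis, so there is no figure to reproduce. The check asks what the contrast would show if STRIDE did nothing.

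**Composition of the comparison group.** Let u be the share of the EHR-defined sample unable to walk and p the penetration. All patients unable to walk fall among the non-walkers, so their share there is u/(1 − p). Only the upper limit p = 40% comes from the protocol; u is assumed.

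- u = 10%, p = 10%: 0.10/0.90 = 11%
- u = 30%, p = 20%: 0.30/0.80 = 37.5%
- u = 60%, p = 40%: 0.60/0.60 = 100% (the extreme corner, where every patient able to walk has been reached)

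**Nursing-home discharge.** Let g be the excess risk in patients unable to walk and a the share of the gap that weighting removes, both assumed. Suppose walkers and missed eligible patients have equal risk. The false difference in STRIDE's favour is then u/(1 − p) × g × (1 − a).

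- Central example, u = 30%, p = 20%, g = 10 points: 0.375 × 10 = 3.75 points with a = 0; 1.9 with a = 0.5; 0.4 with a = 0.9.
- Over u = 10–60%, p = 10–40%, g = 5–20 points: 0.6 to 20 points with a = 0; 0.3 to 10 with a = 0.5; 0.1 to 2 with a = 0.9.

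Sample size gives no protection. With 95,000 Veterans, assumed penetration of 20% and assumed discharge of 10%, the standard error is √[0.10 × 0.90 × (1/19,000 + 1/76,000)] = 0.24 points, ignoring clustering and weighting, both of which would normally enlarge it. A 1.9-point artefact would be about 8 such standard errors.

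**Length of stay.** A second force acts here: a longer stay gives more days on which a first walk can be recorded. This was simulated with 400,000 stays, no STRIDE effect and no weighting. For patients able to walk, stays were gamma (shape 2, mean 5 days, rounded up to whole days) with a constant daily chance of a first walk. For those unable to walk, that chance was zero. All these inputs are assumed.

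| Share unable to walk | Their mean stay, relative to the able | Penetration | Walkers minus non-walkers (days) |
|---|---|---|---|
| 0% | n/a | 15–41% | +2.4 to +2.6 |
| 30% | 1.0 times | 10–28% | about +2.2 |
| 30% | 1.5 times | 10–28% | +1.4 to +1.1 |
| 30% | 2.0 times | 10–28% | +0.6 to 0.0 |
| 60% | 1.5 times | 6–25% | +0.5 to −0.6 |
| 60% | 2.0 times | 6–25% | −1.0 to −2.6 |

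With nothing going on, STRIDE can look harmful, neutral or beneficial. The first row shows that limiting comparators to patients known to walk removes the eligibility problem but not the one about time.

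**Falls.** The documents give no basis for a direction. Patients who cannot walk might fall more or less often than those who can.

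**The case against.** The case for the plan has four parts.

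- **Only some criteria are affected.** A reader might infer that eligibility as a whole cannot be judged from the EHR. The protocol says only that not all criteria can be; age and medical admission are not said to be unassessable. This stands, but the one example given is the criterion that matters most here.
- **The plan does adjust.** Covariates are to be fixed in advance, and GEC Health Care Risk measures are available. They may remove part of the gap. How much is unknown, because no document says they capture ability to walk on admission. This limits the size of the concern; it does not remove it.
- **The analysis is exploratory.** The primary goal is to compare implementation strategies, and that comparison does not depend on this one. This stands and limits the severity.
- **The sizes are assumed.** Adoption needs only five patients with a walk, so pooled penetration could be low and the contamination smaller: u = 10% and p = 5% give 0.10/0.95 = 11%. A reader might also take the 40% ceiling to mean that 60% of the sample cannot walk. It does not show this, since limited program capacity would explain the ceiling equally well.

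Replacing the planned analysis outright with a site-level one would also go too far. It changes the estimand from a per-participant to a site-level effect. The protocol says all current STRIDE sites launched within 10 months, so concurrent unlaunched controls may be scarce. Some hospitals will also have tried mobility programs before, which blurs a pre-launch period.

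**Conclusion.** The concern holds for the causal claim. As written, non-participants may include patients who could not walk, the plan does not say how this would be known, and weighting cannot correct for a determinant that is not recorded. If walking ability is unrecorded, positivity fails and the average causal effect is not identified.

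For nursing-home discharge the bias probably favours STRIDE, assuming patients unable to walk are at higher risk. Its size is unknown: 0.1 to 20 points over the ranges tried, 3.75 points unadjusted and 0.4 points after 90% removal in the central example. It depends on the share unable to walk, their excess risk and what the recorded covariates remove.

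A reader might go further and conclude that STRIDE will look beneficial on every outcome even if it does nothing. The documents do not support that. Length of stay, the effectiveness outcome on which the protocol focuses, is pulled the other way by walks accruing during the stay, and its net sign is unknown. Falls have no documented direction. The randomized penetration comparison is unaffected.

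**What to change.** In both places where the analysis is described (STRIDE Analyses, and Data Analysis and Statistical Considerations):

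1. Replace the claim to estimate an average causal effect with an adjusted association between STRIDE participation and outcome. State that ability to walk cannot be verified for all non-participants.
2. List the recorded mobility and function proxies to be used in the weights. Report overlap of the propensity scores and say how regions of poor overlap are handled.
3. Add a sensitivity analysis for unmeasured walking ability, for example the formula above over stated ranges of u and g, showing what would explain away the observed difference.
4. Add a supporting analysis of all EHR-eligible hospitalizations at adopting sites, before versus after the first documented STRIDE activity, with enrolled sites not yet launched as concurrent controls where available. Unverifiable eligibility is then handled alike on both sides, and exposure is set by site and period, so it does not accrue with length of stay.

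Item 1 is wording; items 2 and 3 need modest analysis time. Item 4 needs a pre-launch extract from sources already in use. Its estimate is a site-level effect diluted by penetration (at most about 40%), relies on parallel trends and may have few control sites, so it should support the participant contrast and not replace it.
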